Our objective is to determine the effect of and compare two different doses of IV dexamethasone given preoperatively before TKA, when compared to placebo, using the outcome measures listed below:

Primary Outcome Measures

- To assess patient reported visual analog pain scores.
- To assess patient controlled analgesic usage.

Secondary Outcome Measures

1. To assess the soft tissue swelling about the operative knee after steroid administration.
2. To assess postoperative glucose levels after steroid administration.
3. To assess rehabilitation parameters such as postoperative knee range of motion and time to physical therapy clearance.
4. To assess incidence of nausea and vomiting postoperatively after steroid administration.
5. To assess patient satisfaction and function scores at 4 months with both Short Form (SF) – 12 and Knee Injury and Osteoarthritis Outcome Score Short Form (KOOS, Jr.) scores.
6. To assess hospital admission characteristics such as length of stay and rate of readmission.
7. To assess the risk of infection at 4 months and wound drainage at 7 days after perioperative steroid administration in total knee arthroplasty.

Study Design and Methods

We plan to conduct a prospective, double-blinded, randomized, placebo-controlled trial to evaluate perioperative glucocorticoid administration in total knee arthroplasty. There will be three arms in the study: 1) Placebo, 2) 10 mg dexamethasone, and 3) 20 mg dexamethasone.

Consent to Participation in the Study

Patients will be given the opportunity to participate in the study at the time of consent for surgery and blood product, which typically takes place in clinic during an evaluation for severe end-stage arthritis. It will be emphasized that study participation is optional, and that patients may be randomized to the control or placebo group. Patients will sign the combined informed consent and HIPAA form in order to participate in the study.

Method of Randomization

Once a patient chooses to be part of the study, he/she will be randomized in a blocked fashion to either the control group or to one of two intervention groups. Randomization will occur after informed consent has been obtained from the patients and after the preoperative screening examination is complete. Patients and investigators will be blinded to the randomization assignment. Emory's Investigational Drug Services will randomize each patient prior to dispensing the blinded dexamethasone/placebo doses.

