Therapeutic Intervention

Patients in the intervention arms will receive two doses of either 10 mg dexamethasone or 20 mg dexamethasone. The first dose will be administered preoperatively within three hours of surgery once the patient receives anesthesia. The second dose will be administered eight hours after the first dose in the inpatient setting by the nurse in that unit. The second dose will be administered using a piggyback setup. Patients in the placebo arm will receive two doses of saline/placebo.

This particular dosing is chosen based on available literature that suggests a safe and effective dose is between 4 and 20 mg of dexamethasone²⁵⁻²⁶.

The administration of either steroid or placebo will occur in a double-blinded fashion. For each study participant, two blinded doses will be sent over from Emory's Investigational Drug Service (IDS). Thus, neither the patient receiving the medication nor the health care professional administering the medication or collecting study outcome data will be aware of whether or not the patient received the steroid or the placebo.

Both the intervention and control groups will receive spinal anesthesia using lidocaine and a standard multimodal postoperative pain management regimen typically used for total knee arthroplasty. This regimen will be standardized across all three attending surgeons participating in the study. The standard multimodal pain management regimen will be as follows:

- Preoperative:
 - **Decadron: 10 or 20mg IV x 2 doses, 8 hours apart (if randomized to study group)**
- Intraoperative:
 - **Ropivacaine:** Given intraoperatively. Injection, subcutaneous tissue/skin. Administered in standard fashion. (300mg)
 - **Toradol:** 30mg q 6hr for 6 total doses. 1st dose given intraoperatively at incision. (15 mg if patient is >65 years of age. Patients with Cr >1.5 will not receive Toradol).
- Postoperative
 - **Tylenol:** 1000mg po q 8hr (scheduled)
 - **Oxycodone:** 5mg or 10mg q 3-4hr prn pain, If intolerant to Oxycodone: second agent line is Hydrocodone or Oral Dilaudid (Tylenol will be adjusted accordingly if patient receives Hydrocodone).
 - **IV Morphine (or Dilaudid):** 1 or 2 mg q 2hr prn breakthrough pain
 - **Morphine PCA:** only for failure of the above
 - **MS Contin:** 15 mg BID for two weeks

On postoperative day (POD) 1, patients will be transitioned to oral (PO) and intravenous (IV) medications on an as-needed basis with a regimen that will be standardized across all study participants.

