After the study is complete, statistical analysis will be performed using de-identified patient data to determine differences in primary and secondary outcomes. Repeated-measures analyses for VAS pain score (and change from baseline), knee ROM, functionality scores (SF-12 and KOOS, Jr.), and blood glucose will be done with a means model with SAS Proc Mixed (version 9, mixed linear models) providing separate estimates of the means by time on study (baseline, in hospital, day 7, and at 1,4 and 12 months after total knee arthroplasty) and treatment group (dexamethasone or control). A compound symmetry variance-covariance form among the repeated measurements will be assumed for each outcome and robust estimates of the standard errors of parameters will be used to perform statistical tests and construct 95% confidence intervals²⁶. T-tests will be used to compare the pairwise differences between the model-based treatment means (least-squares means) at each time point. Mean changes over time within a treatment group will be tested for linear trend. The model-based means are unbiased with unbalanced and missing data, so long as the missing data are non-informative (missing at random). A

dropout process is assumed to be missing at random if, conditional on the observed data, the dropout is independent of the unobserved measurements. Statistical tests will be two-sided. A p value < 0.05 will be considered statistically significant.

Adverse Event Reporting

At a six-month time point following initiation of the study, we will assess our results for any reportable adverse events, including postoperative infections. This data will be reported to the Emory Institutional Review Board (IRB). We will monitor for any adverse outcomes at each subsequent six-month interval.

Data Safety and Monitoring Plan

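### Three surgeons operate but surgeon is neither a stratum nor a model term, so any surgeon differences stay in the error of the modelled comparisons: a modest loss of precision, not a bias

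*Combined protocol and SAP*

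**What the plan says.** Under Method of Randomization, once a patient agrees to take part, "he/she will be randomized in a blocked fashion to either the control group or to one of two intervention groups". The drug service carries out the allocation: "Emory's Investigational Drug Services will randomize each patient prior to dispensing the blinded dexamethasone/placebo doses". No block size, stratification factor or surgeon-level list is given. The design has three arms: "There will be three arms in the study: 1) Placebo, 2) 10 mg dexamethasone, and 3) 20 mg dexamethasone".

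Under Therapeutic Intervention, the protocol describes spinal anaesthesia and a multimodal pain regimen for all groups and adds: "This regimen will be standardized across all three attending surgeons participating in the study".

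Under Statistical Analysis, the mixed model is described as "providing separate estimates of the means by time on study" "and treatment group (dexamethasone or control". The outcomes named are "Repeated-measures analyses for VAS pain score (and change from baseline), knee ROM, functionality scores (SF-12 and KOOS, Jr.), and blood glucose". Arms are then compared as follows: "T-tests will be used to compare the pairwise differences between the model-based treatment means (least-squares means) at each time point". No surgeon term or other covariate is listed, and there is no sensitivity analysis by surgeon.

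**The concern.** Blocking without strata balances the total size of the arms. It does not balance the arms within each surgeon's caseload. If patients' mean outcomes differ by surgeon, that variation is part of the residual in an analysis that ignores surgeon, and it enlarges the standard error of each contrast the model produces.

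Surgeon should normally be known before allocation, because consent is sought at the preoperative clinic visit and randomization follows. A factor that is known in advance and costs two degrees of freedom is a natural candidate for adjustment. Prespecifying it also prevents an argument, once the data are seen, about whether to adjust for an imbalance that happened to appear.

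**Working it through.** **Inputs from the documents.** Three surgeons; three arms of 47; two-sided 0.05; 90% power; planned VAS difference 1.5 per dose step. **Assumed, because the documents give no figure:** the VAS standard deviation, the spread of surgeon means, and equal surgeon caseloads.

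**1. The plan's own figure.** The sample size cannot be reproduced outright because no SD is stated. Solving backwards for a two-sample t-test with 47 per arm, difference 1.5 and 90% power gives SD = 2.22 (the normal approximation gives 2.22 to 2.24). The standard error of a pairwise difference is 2.22 × √(2/47) = 0.458, about 0.46. The total checks: 3 × 47 = 141.

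**2. Surgeon share of variance.** Put the surgeon means at −s/2, 0 and +s/2 with equal caseloads. The between-surgeon variance is s²/6, and its share of the total is (s²/6)/2.22².

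**3. Gain from adjustment.** The residual SD becomes 2.22 × √(1 − share), and the equivalent sample size per arm is 47/(1 − share).

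| Surgeon spread s (assumed) | s²/6 | Share of variance | Equivalent n per arm | Power for 1.5 points |
|---|---|---|---|---|
| 1.0 | 0.167 | 3.4% | 48.6 | 91.0% |
| 1.5 | 0.375 | 7.6% | 50.9 | 92.1% |
| 2.0 | 0.667 | 13.5% | 54.4 | 93.6% |

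Adjustment is therefore worth about 2 to 7 patients per arm over this range. Expressed by share directly (SD 2.24, normal approximation), power is 90.4% if surgeon explains 1% of the variance, 91.5% at 5% and 92.8% at 10%.

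**4. Chance shift in a pain contrast.** Without a surgeon term, the shift due to surgeon mix has SD √((2/47) × s²/6).
- s = 1.0: √(0.04255 × 0.1667) = 0.084. In simulation, 95% of trials lie within about 0.16 points.
- s = 2.0: √(0.04255 × 0.6667) = 0.168. In simulation, 95% lie within about 0.32 points.

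Multiplying by 1.96 gives 0.165 and 0.330; the small difference from simulation comes from whole-number caseloads.

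This shift is already inside the unadjusted standard error. For s = 1.0, 0.084² = 0.0071, and 0.0071/0.458² = 3.4%, the share found in step 2.

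**5. How often the surgeon mix differs visibly.** For one surgeon and one pair of arms, the SD of the difference in share is √(2 × (1/3)(2/3)/47) = 0.097, or 9.7 percentage points. Simulating 40,000 trials of 3 × 47, the chance of a difference of 15 points or more is:
- about 10% for one given surgeon in one given pair of arms;
- about 23% for some surgeon in one given pair (26% if blocks of 6 are assumed, which leaves the last block incomplete and the arms slightly unequal);
- about 46% for some surgeon in any of the three pairs.

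**6. Covariate without stratification.** With a surgeon term but no stratified blocks, the variance of a pairwise contrast averages about 1.5% above that under perfect balance (95th percentile about 4.4%). This is also the price of the term if surgeons do not differ at all.

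**The case against.** The strongest reply is that nothing here is an error. Unstratified blocked randomization is valid, the trial runs at one hospital, and the protocol standardizes anaesthesia and analgesia across the surgeons, which should narrow differences in the pain and analgesic outcomes that matter most. The 94% power figure needs surgeon means 2.0 VAS points apart, more than the 1.5 the trial plans to detect between dose steps. At 1.0 point the gain is one percentage point of power. All of this stands, and it is why the point is minor.

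Four stronger readings are tempting, and the documents support none of them.
- A reader might infer bias or invalid tests. Allocation is random, so imbalance in surgeon mix is chance variation, which the unadjusted confidence interval already covers.
- A reader might count chance imbalance and wider intervals as two problems. Step 4 shows they are the same variance seen twice.
- A reader might extend the point to every comparison in the trial. The model is written only for the outcomes listed above. Opioid use, swelling, therapy clearance and length of stay have no stated model to which a term could be added.
- A reader might infer that technique or discharge practice varies between surgeons. The protocol is silent on this, and silence is not evidence of variation. Physical therapists, not surgeons, judge therapy clearance.

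It is also possible that the drug service holds a list stratified by surgeon; the protocol does not say so.

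**Conclusion.** The point holds as a modest, avoidable loss of precision in the modelled comparisons. For pain, with surgeon means 1.0 to 2.0 VAS points apart, adjustment moves power from 90% to between 91% and 94%. Against that, the term costs about 1.5% in variance if surgeons are alike.

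The size rests on three assumptions: an SD of about 2.22 back-solved from the stated sample size, equal caseloads, and a surgeon spread that the documents do not give. The figures are for a single time point; a surgeon main effect in the repeated-measures model delivers them only so far as surgeon differences are stable over time. The benefit could be larger or smaller for ROM and the other outcomes, and nothing in the documents lets one say which. Severity: the sponsor could make this change; the trial's conclusions do not depend on it.

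**What to change.** Under Statistical Analysis, prespecify before unblinding that attending surgeon (three levels) enters the mixed model as a fixed effect, alongside time and treatment group. State that surgeon will also be included in whatever models are chosen for the other continuous outcomes. In the same edit, reconcile the treatment term, which the model sentence describes as dexamethasone or control, with the three arms of the design. The cost is two degrees of freedom and recording the surgeon for each patient; no extra patients, visits or staff are needed.

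If allocation has not begun, the permuted blocks could also be stratified by surgeon. This is optional: the covariate alone gives nearly all the gain, and stratifying means three pharmacy lists instead of one and up to three incomplete final blocks. If enrolment has begun, add only the model term. If the list is already stratified by surgeon, say so under Method of Randomization and keep surgeon in the model.

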
Data Collection

Data will be collected by a number of different health professionals during enrollment, during the patient's postoperative hospital stay, by smart device application (app), and during the patient's routine postoperative follow up visits (1 month, 4 months, and 12 months). After surgery, no participants in any group will be subjected to any extra invasive tests or interventions related to their involvement in the study. Patients will not be informed whether or not they have received the study

drug until after all data collection is complete. The schedule of study activities and data collection are shown in Table 1.

1. **Pain assessment:** Postoperative pain will be assessed using the well-standardized and accepted visual analog pain scale. This data will be recorded at baseline, during the hospital stay, and at all follow-up visits. A smart device app will be used to record this information for the 7-day postoperative period. Questions will be asked morning, afternoon, and evening for every patient. Patients enter alarms for morning, afternoon, and evening the first time they use the app. Patients can later adjust these alarms if necessary. Timestamps will be recorded for each of these entries as patients will be asked about their 'average' pain over the preceding 4 hours, and they will be able to edit/modify prior entries at any time. Patients will also be asked during the first entry for the day if they were awoken from pain or nausea during the previous night, and if they click yes, they will be prompted to select pain scores corresponding to this event. There will be a comments section to provide patients the ability to enter text. Furthermore, during the hospital stay this data will be recorded with each vital sign assessment by the nursing per standard of care. The following scale will be used to assess pain:

[figure not shown]
©1983 Wong-Baker FACES® Foundation. www.WongBakerFACES.org
Used with permission.

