2. **Opioid analgesic usage:** The amount of each patient's postoperative opioid analgesic usage (converted into milligrams of morphine equivalents per day) will be recorded throughout the duration of their hospital stay. After inpatient discharge, this data will be collected using the smart device app. Patients will track the use of both prescribed narcotic medications and over the counter non-steroidal anti-inflammatory medications use for knee pain. Once patients are discharged from the hospital, they will be asked each day to enter their medication usage from a preloaded list (number of pills/day). Patients may also choose to enter other medications not on the list. This information will be recorded for the two-week postoperative period.
3. **Soft tissue swelling:** Soft tissue swelling will be evaluated using a measurement of knee circumference at the midpoint of the patella, with the knee in the maximum amount of extension allowed by the patient. This

measurement will be completed twice, and the average of the two measurements will be used as the value for that day. Knee circumference will be measured at baseline (time of enrollment), at POD 1 and each subsequent in-hospital POD, and at each follow up visit. The measurements obtained at baseline and at each clinic visit will be conducted by the research coordinator or physician. Postoperative measurements obtained during the patient's hospital stay will be conducted by the physical therapy staff, during the first/morning therapy session of each day. The non-operative knee will also be measured at the time of enrollment to use as a reference.

4. **Range of motion (ROM):** maximum active and passive ROM allowed by the patient will be measured using a goniometer. This measurement is the amount of flexion and extension recorded in degrees. ROM will be measured at the following time points: preoperatively at baseline, at POD 1 and each subsequent in-hospital POD, and at each follow up visit. ROM will be measured on postoperative in-hospital days by a physical therapist, whereas ROM at clinic visits will be measured by the research coordinator or physician. If more than one ROM measurement is obtained during an inpatient day, the numbers will be averaged to create one value for that day.

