7. **Blood Glucose Levels:** The patient's blood glucose level will be recorded once preoperatively at the pre-anesthesia clinic visit several days before surgery, at POD 1 and at each subsequent in-hospital POD using a hemocue. These do not consist of extra blood tests, as blood draws at these time points are considered standard of care. This data is being collected because hyperglycemia is a potential complication of IV steroid use. If patients experience ketoacidosis or hyperglycemia greater than 300, the study drug/placebo will be discontinued.
8. **Functionality scores:** The Short Form (SF) – 12 and Knee Injury and Osteoarthritis Outcome Score Short Form (KOOS, Jr.) questionnaires will be administered to patients at the baseline visit and at each follow up clinic visit. Both of these standardized function questionnaires are well validated and widely accepted in the literature.
9. **Hospital length of stay and readmission:** We will record the length of each patient's hospital stay and any readmission to our hospital for the 12-month duration of study.
10. **Infection:** Patients will have standard follow up clinic appointments at 1 and 4 months after surgery, at which time the clinical presence of possible wound drainage and periprosthetic infection will be evaluated. Patients will be followed up to 1 year after surgery to monitor for latent infections.

Table 1: Outcome measure and data collection schedule

	Pre-operative clinic visit	Each inpatient day	7 day app usage	2 week app usage	1 month clinic visit	4 month clinic visit	12 month clinic visit
Consent, Enrollment, Randomization	X						
Pain assessment	X	X	X		X	X	X
Opioid usage		X					
Pain medication log			X	X			
Knee swelling	X	X			X	X	
Knee ROM	X	X			X	X	X
Physical therapy milestones		X					
Nausea/vomiting		X	X				
Blood glucose	X	X					
Postoperative infection/Wound drainage		X			X	X	X
Length of stay		X					
KOOS, Jr. and SF-12	X				X	X	X

Consent Process

Patients will be asked to participate in the study at a preoperative clinic visit. The risks, benefits and the optional nature of the study will be emphasized. Patients may withdraw from the study at any given time. Consent will be obtained from one or more of the following three people: the attending surgeon, the orthopaedic surgery resident, or the research coordinator.

Participant Selection

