This study will be conducted at Emory University Orthopaedic and Spine Hospital and Clinic. The investigators perform over 500 total knee arthroplasty procedures per year. We estimate 75% (375) of the patients will be eligible and be willing to participate in the study. The Department of Orthopaedics staff performs 10-20 clinical trials per year and therefore is well-trained and prepared to perform clinical trials of this magnitude.

Inclusion Criteria

1. Patients undergoing primary total joint arthroplasty of the knee
2. Adult patients ages 18-100 years
3. Patients must have smart phone and/or device for app usage

Exclusion Criteria

1. Current chronic steroid use
2. Patients undergoing revision knee surgery
3. Patients ambulating preoperatively with assistive devices
4. Patients with avascular necrosis of the operative knee
5. Patients with a history of an adverse reaction to glucocorticoid steroids
6. Patients unable to provide informed consent
7. Patients with inflammatory arthritis
8. Prisoners
9. Current smokers
10. Patients <18 years of age
11. Any patient with a complicated postoperative course that requires transfer to the Intensive Care Unit (ICU) or to another facility for further management will be removed from the study.
12. Any contraindication that would prevent the patient from being treated with the standard multimodal postoperative pain management regimen
13. History of infection of surgical knee.
14. Patients with diabetes.
15. Patients that have an intolerance to Toradol.
16. Patients that do not have smart phone and/or device for app usage

Statistical Analysis

In order to adequately examine our primary outcome measure of pain reduction, our target sample size was obtained by a power analysis using retrospective data. Assuming a mean difference in the VAS of 1.5 between placebo vs. low dose and 1.5 for low dose vs. high dose (or 3 between placebo and high dose), in order to achieve 90% power, we will need 47 patients per study arm. Thus, the total number of patients enrolled would need to be at least 141. Based upon historical data, we expect it to take 18 months to reach our target N of 141.

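### No preoperative opioid value is planned, so the opioid primary outcome forgoes precision that one baseline question could recover

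*Combined protocol and SAP*

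**What the plan says.** Primary Outcome Measures lists two items: visual analog pain scores, and "To assess patient controlled analgesic usage". Data Collection, item 2 gives the measurement: "postoperative opioid analgesic usage (converted into milligrams of morphine equivalents per day) will be recorded throughout the duration of their hospital stay". After discharge, patients log their medication in the app: "This information will be recorded for the two-week postoperative period".

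In Table 1 the opioid usage row is marked only for inpatient days, and the row "Pain medication log" only for the two app periods. The pre-operative visit column is marked for pain, swelling, range of motion, glucose, KOOS, Jr. and SF-12. Of pain, item 1 says: "This data will be recorded at baseline, during the hospital stay, and at all follow-up visits". Nothing equivalent is said of opioids.

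The only medication whose chronic use is excluded is steroids ("Current chronic steroid use"). The nearest other criterion is number 12: "Any contraindication that would prevent the patient from being treated with the standard multimodal postoperative pain management regimen". It does not name opioid use, and the standard regimen itself contains opioids.

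Method of Randomization describes blocked allocation and names no stratification factor. Statistical Analysis specifies "Repeated-measures analyses for VAS pain score (and change from baseline), knee ROM, functionality scores (SF-12 and KOOS, Jr.), and blood glucose". It does not list opioid use and names no prognostic covariate.

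**The concern.** The patients have end-stage arthritis, so it is plausible that some take opioids before surgery, although the documents give no rate. Patients who did so may well use more afterwards for reasons unrelated to the study drug. Because the outcome is a postoperative total with no baseline value beside it, that difference between patients goes into the residual variance of a primary outcome.

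Pain, the other primary outcome, has a baseline and a planned change-from-baseline analysis. The opioid outcome has neither. The baseline pain score is an imperfect substitute, since pain reported while taking opioids may already be reduced by them. What is at stake is the width of the confidence intervals, and so the power, for the opioid comparisons. The documents show no sample-size margin for this outcome, because the 47 per arm was derived from VAS pain alone.

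**Working it through.** **The plan's own figure.** The only sample-size figure is 47 per arm (3 × 47 = 141), for a VAS difference of 1.5 at 90% power; the tests are two-sided at 0.05. No standard deviation is stated. Solving for it: SD = 1.5 / [(1.960 + 1.282) × √(2/47)] = 2.24. The figure can be matched only by choosing that SD, so it is neither confirmed nor refuted. It says nothing about opioid use, for which the documents give no SD, target difference or power.

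**Step 1: what adjustment could gain.** Assume prior use explains a share R² of the variance in postoperative opioid use. This is not a document figure. The adjusted interval is √(1 − R²) times the width of the unadjusted one, and the equivalent gain in sample size is 1/(1 − R²).

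| Assumed R² | Adjusted / unadjusted width | Narrowing from adjustment | Excess width without it, 1/√(1 − R²) − 1 | Sample-size factor |
|---|---|---|---|---|
| 0.10 | 0.949 | 5% | 5% | 1.11 |
| 0.20 | 0.894 | 11% | 12% | 1.25 |
| 0.30 | 0.837 | 16% | 20% | 1.43 |

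**Step 2: the same loss expressed as power.** Let p be the share of prior users and D their shift in postoperative use, in units of the SD within the user and non-user groups. Both are assumed: p = 10% to 40%, D = 0.5 to 1.5. Leaving prior use out inflates the variance by V = 1 + p(1 − p)D². Take a pairwise comparison that would have 90% power with the covariate and 47 per arm. Power without it is Φ(3.242/√V − 1.960), and the number per arm needed to compensate is 47V, rounded up.

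- p = 10%, D = 0.5: V = 1.0225, power 89%, 49 per arm.
- p = 30%, D = 1.0: V = 1.21, power 84%, 57 per arm.
- p = 40%, D = 1.5: V = 1.54, power 74%, 73 per arm.

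The corresponding R² is (V − 1)/V: 0.02, 0.17 and 0.35.

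**Step 3: chance imbalance is not an additional harm.** The arm difference in the proportion of prior users has SD √(2p(1 − p)/47). For p = 15%, 25% and 35% this is 0.074, 0.089 and 0.098, giving 95% ranges of ±14, ±17 and ±19 percentage points. In the units of step 2, the variance of the unadjusted treatment difference is (2/47) × [1 + p(1 − p)D²]. The second term, 2p(1 − p)D²/47, is exactly the variance due to that imbalance. It is therefore already in the standard error and is the same loss as in steps 1 and 2. It must not be counted again.

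**The case against.** A reader might infer that unrecorded prior use biases the comparison, or produces a false opioid-sparing effect beyond the nominal error rate. The documents do not support this. Allocation is randomised and double-blind, so there is no bias in expectation, and step 3 shows that chance imbalance is already covered by the standard error and the two-sided 0.05 level.

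A reader might also infer that the gap can never be repaired. That is too strong. Table 1 is not exhaustive: age and sex sit in the subject key, and readmissions and adverse events are collected without a row of their own. Applying the steroid exclusion already requires asking about current medication. The medical record number is kept, so a chart search is not ruled out. What stands is narrower: no baseline opioid value is planned, and the documents do not say that charts hold a usable dose.

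Nor do the documents show that a patient's habitual dose is added one for one to the postoperative total. All patients receive a standardised regimen that includes scheduled and as-needed opioids. The text does not say whether home opioids continue alongside it, and criterion 12 might remove some such patients. The predictive strength of prior use is therefore plausible but unquantified.

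Finally, the outcome has more basic gaps. The objective refers to patient-controlled analgesia, which the regimen reserves for failure of the other agents, while item 2 counts all opioids. I treat these as one outcome, but the wordings need to be reconciled. The analysis section also specifies no opioid comparison to which a covariate could be added. Both criticisms are fair. They widen the fix and do not remove the point.

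**Conclusion.** The point holds as a cheap improvement in precision. It is not an error that threatens the trial's validity. Three facts are clear from the text: total postoperative opioid use serves as a primary outcome, prior opioid use is not an exclusion, and no preoperative value is scheduled.

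The size of the loss is unknown, because every input beyond 47 per arm is assumed. If prior use explains 10% to 30% of the variance, adjustment narrows intervals by 5% to 16%. On the wider grid of step 2, a comparison with 90% power when adjusted has 74% to 89% without adjustment. The mild end is trivial. The severe end is material, but it needs 40% prior users and a shift of 1.5 SD. The R² formula also assumes a roughly linear relation between prior and postoperative use.

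**What to change.** 1. In Table 1, mark opioid use in the pre-operative clinic visit column. Record each patient's daily opioid dose over the preceding month, in morphine equivalents, before randomisation.
2. If patients are already enrolled, recover the value from preoperative records where possible, before unblinding, and flag its source.
3. In Statistical Analysis, add opioid use to the analysed outcomes, and prespecify the preoperative dose as a covariate in the between-arm opioid comparisons, with its functional form and the handling of missing values.
4. Use one wording for the outcome in Primary Outcome Measures and in Data Collection, item 2.

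Leave eligibility unchanged. The cost is one question at a visit that already takes place, one form field and one model term. The downside is that the value is partly self-reported, and values recovered from charts may be incomplete.
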